7.1.3 The Window of Analysis

For visits after baseline, all analyses will be conduct based on the scheduled visit in the protocol, and the unscheduled visits will not be included in the summary tables but be included in the listings.

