# 9.1.6 Blood sample and urine sample collection

Blood samples will be collected at each site visit: ie, at Screening Visit for eligibility screening tests (clinical laboratory testing, see Section 9.1.6.3), at Visits 2, 3 and 6 for routine safety laboratory testing (see Section 9.1.6.4 for Visits 2, 6 coagulation function test, Visits 2, 6, 11 thyroid function test). Blood samples for immunogenicity (anti-S1/anti-RBD IgG and SARS-CoV-2 neutralizing antibody) will be collected at Visits 1, 5, 6, 8, 10, 11 and 12 for adults and at Visits 1, 5, 6, 8, 11 and 12 for the elderly (see Section 9.1.6.5).

Should a blood sampling be performed during a vaccination visit, this sampling must occur before the injection of the investigational vaccine or placebo. Serum sample will be collected for women of childbearing potential at Screening Visit and Visit 5 before each investigational vaccine/placebo injection for pregnancy testing (see Section 9.1.9). Figertip blood samples will be collected at Screening Visit for SARS-CoV-2 serostatus determination (see Section 9.1.6.1) and HIV serostatus determination (see Section 9.1.6.2).

Urine samples will be collected for all subjects at Screening Visit for eligibility screening (see Section 9.1.6.3), and at Visits 2, 3 and 6 for routine safety laboratory testing (see Section 9.1.6.4).

All samples will be collected in accordance with acceptable laboratory procedures. Samples of immunogenicity and CMI testing will be processed and stored at the study site as described in the provided Laboratory Manual.

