# 9.1.6.3 Screening laboratory testing

Screening laboratory testing that will be performed on blood and urine samples at Screening Visit are outlined in **Table** 4.

Subjects of adults must have laborat ory values within normal limits or not be above Grade 1 as defined in Appendix B within 7 days before enrollment, and Grade 2 for the elderly. If the results of laboratory screening testing are out of acceptable range, repeat of screening tests is permitted once, provided there is an alternative explanation for the out of normal range value.

Should the respective repeated test results be available within the screening period, no new subject screening numbers will be required; the repeated screening tests will be recorded in the appropriate CRF (unscheduled lab form). Should the respective repeated test results not be available within the screening period, the subject would need to be screen failed and all screening procedures and tests would need to be repeated with a new subject screening number.

Blood samples for screening laboratory testing will be approximately 15 mL.

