# 10.4 Follow-up of adverse events

The investigator should follow up each adverse event. The laboratory test of clinical indicators shall be retested in time if there are  $\geq$  Grade 1 or clinically significant abnormal items judged by the investigator. For all SAEs and AEs with relevance which still exist until the end of AE/SAE collection and record, the investigator should follow up to:

- The event is solved or resumes to the status of baseline or is stable:
- The investigator can confirm that there will be no further improvement;
- No more information can be obtained (the subject refuses to provide more information, or there is evidence which proves that the subject is lost to follow-up even if the investigator has tried his/her best).

During the study, the recovery time (with date) of adverse event should be recorded in AE eCRF and the patient's medical record to verify the original data.

For serious adverse events, adverse events of special interest and pregnancy events, the Fosun or other designated personnel can obtain more case information through telephone, fax, e-mail and/or supervising to perform independent medical assessment for these cases.

The AE original data records updated after the lock of database are available for backup. SAE information needs to be filled in the Serious Adverse Event Report Form as detailed as possible, which is reported to PV department.

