#### 13.1.6 Safety analysis

#### Clinical laboratory parameters

Clinical laboratory parameters at each timepoint and change from baseline to each post-baseline time point will be summarized using descriptive summary statistics for each parameter by group.

Shift tables from baseline to worst intensity grade will be provided for each laboratory parameter by group. Make a list and descriptive summary from normal baseline to post-vaccination abnormality, or from abnormal baseline to post-vaccination enhancement of severity.

Additionally, the occurrence of clinically significant abnormal laboratory results within a trial subject will be analyzed using descriptive summary statistics for each parameter and visit by group.

Laboratory parameter results will be listed along with the normal ranges. Values that are below or above the normal ranges will be flagged.

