7.6.2 Laboratory Assessments

Descriptive statistics for quantitive laboratory parameters at each time point and change from baseline will be provided by group.

Shift tables from baseline to the worst intensity grade will be provided by group for each gradable laboratory parameter, where low/normal/high or abnormal not clinically significant/ abnormal clinically significant /normal status had been ascertained.

Also, shift tables from baseline to the worst laboratory abnormality grade will be provided by group for each gradable laboratory parameter (if applicable), where laboratory abnormality grade is calculated according to the Appendix C Table 4: *Laboratory abnormality grading scale*.

Additionally, the occurrence of clinically significant abnormal laboratory results will be provided for each parameter and visit by group.

All of laboratory assessments will be listed by subject along with the normal ranges. Values that are below or above the normal ranges will be flagged.

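### SAP 7.1.3 bars unscheduled results from summary tables, so the worst-grade laboratory shift tables can miss a retest that is worse than every scheduled value

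*SAP*

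**What the plan says.** SAP 7.1.3 sets a general rule: "For visits after baseline, all analyses will be conduct based on the scheduled visit in the protocol". It adds that "the unscheduled visits will not be included in the summary tables but be included in the listings". No exception is given.

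SAP 7.6.2 plans two laboratory displays that look for a worst value:
- The first reads "Shift tables from baseline to the worst intensity grade will be provided by group for each gradable laboratory parameter" and is based on low/normal/high status or on clinical-significance status.
- The second, graded by Protocol Appendix C Table 4, reads "shift tables from baseline to the worst laboratory abnormality grade will be provided by group". The SAP version history shows that Version 1.1 was issued to add this Appendix C analysis.

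Protocol 13.1.6 has the parent analysis: "Shift tables from baseline to worst intensity grade will be provided for each laboratory parameter by group". It does not restrict that table to scheduled visits. SAP 2.3 declares no departure from the protocol's analyses.

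On data collection, Protocol 10.4 says "The laboratory test of clinical indicators shall be retested in time if there are" results of Grade 1 or above, or abnormalities that the investigator judges clinically significant. Protocol 9.1.6 places blood sampling "at Visits 2, 3 and 6 for routine safety laboratory testing", with coagulation at Visits 2 and 6 and thyroid function at Visits 2, 6 and 11.

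**The concern.** The SAP tells the programmer to tabulate each subject's worst laboratory grade and also to leave out a class of results that the protocol requires precisely because an earlier result was abnormal. If both instructions are followed, the table shows the worst scheduled grade under the label of worst grade.

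Safety is the primary objective, and the shift tables are the main aggregate view of laboratory change without symptoms. The adverse event tables only partly cover the same ground. Protocol 10.1.1 counts laboratory abnormalities as adverse events when they have clinical manifestations. It leaves out transitory effects of the known mechanism where the investigator sees no manifest clinical risk or evidence of lasting harm. A retest that worsens without symptoms could therefore appear in no summary table.

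**Working it through.** The plan gives no figure on this point. The only probability in its sample-size section, 86.5%, reproduces as 1 − 0.92^24 = 0.8648. It concerns seeing at least one TEAE in 24 subjects and says nothing about retests, so it is not used here.

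**Step 1: which results fall outside the schedule.** Inputs are the schedules of activities in Protocol Table 2 and Protocol 9.1.6.

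| Tests | Scheduled after baseline | Next scheduled draw after Visit 6 |
|---|---|---|
| Hematology, chemistry, urine | Visits 2 (24 h), 3 (Day 8), 6 (Day 29) | none |
| Coagulation | Visits 2, 6 | none |
| Thyroid | Visits 2, 6, 11 | Visit 11 (Day 184) |

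For hematology, chemistry and urine:
- Abnormal at Visit 2: Visit 3 follows 6 days later (Day 2 to Day 8) and may serve as the recheck. If so, that value is counted.
- Abnormal at Visit 3: Visit 6 is 21 days later (29 − 8 = 21), so a prompt retest falls between scheduled draws.
- Abnormal at Visit 6: no later draw is scheduled, so any retest is outside the schedule.

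**Step 2: direction of the error.** Let S be a subject's highest grade over scheduled draws and U the highest grade over unscheduled draws. The table under SAP 7.1.3 reports S. The label promises max(S, U). Since max(S, U) ≥ S always, the reported grade is either right or too low. It is too low exactly when U > S.

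Enumerating grades 0 to 4 for three scheduled draws and one retest gives 5^4 = 625 patterns. S exceeds max(S, U) in none of them. U exceeds S in 0 + 1^3 + 2^3 + 3^3 + 4^3 = 100. These are counts of possible patterns, not probabilities; they confirm the direction and give no frequency.

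**Step 3: a case the documents make concrete.** Protocol 4.2.4.1 reports Grade 2 neutropenia 6–8 days after the boost in one US subject each at 10 µg and 30 µg. Visit 6 falls at that time and is the last scheduled hematology draw. If such a count reached Grade 3 on the required retest, the shift table would still show Grade 2. The documents do not say that this happened; both subjects were followed without clinical manifestations.

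**Step 4: size.** The number of understated grades is the number of subjects with U > S. That needs the rate of worsening on retest, which the documents do not give. The lower bound is zero.

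**The case against.** The strongest reply is that little depends on this. The study is descriptive with no formal testing. The secondary laboratory endpoint is defined at Hour 24 and Day 7 after the prime and Day 7 after the boost, which are the scheduled draws, so scheduled data measure it as written. Unscheduled results remain in by-subject listings with out-of-range values flagged, and about 24 subjects per group can be read by eye. A retest that shows recovery changes nothing. Symptomatic worsening would enter the adverse event tables, which are built on events rather than visits. All of this stands, and it limits the point to the worst-grade and worst-status shift tables.

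It is also fair that Protocol 10.4 gives no retest interval and names no form. The unscheduled laboratory form is mentioned only for repeat screening tests (Protocol 9.1.6.3). That post-vaccination retests are stored as unscheduled visits is an inference from the schedule, strongest after Visit 6.

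Finally, using all values gives more draws to subjects with a first abnormality, so ascertainment becomes unequal. That is a real but small cost, and it does not justify labelling a partial maximum as the worst grade.

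Three stronger readings are tempting and are not supported:
- **A headcount.** A reader might apply the US lymphocyte rate at 30 µg, 5/11, to 24 subjects (24 × 5/11 = 10.9) and infer about 11 hidden results per group. That would count possible retests, not understated grades. Protocol 4.2.4.1 does not grade all five decreases and says that they were transient and normal by 6–8 days.
- **A biased secondary endpoint.** Its definition at scheduled times rules this out.
- **More bias at the higher dose.** This would need more worsening on retest at that dose, and no such data are given.

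**Conclusion.** The conflict is real and rests on the wording. SAP 7.1.3 excludes unscheduled post-baseline results from every summary table, while SAP 7.6.2 and Protocol 13.1.6 promise a worst grade. Under the rule as written, a retest worse than every scheduled value is missing from those tables, and the error can only understate toxicity. The size is unknown and may be nil.

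The conclusion assumes that retests after vaccination are recorded as unscheduled visits and that SAP 7.1.3 is applied literally. It does not reach baseline: SAP 7.1.2 takes the last available value before the prime immunization, so a repeat before the first dose can still count. Confidence is high on the conflict and on the direction; nothing can be said about frequency.

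**What to change.** Amend SAP 7.1.3 and add a matching line to SAP 7.6.2:
- By-visit laboratory summaries, including the by-visit occurrence of clinically significant abnormalities, use scheduled visits only.
- Worst-grade and worst-status laboratory shift tables use all post-baseline results, including unscheduled and repeat tests.
- A footnote to those tables states that subjects with a first abnormality may have had more draws than others.

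If the sponsor prefers to keep the present rule, the tables should be relabelled as worst grade at scheduled visits, and the departure from Protocol 13.1.6 should be declared in SAP 2.3.

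The cost is one or two sentences and a small programming change. The unscheduled results are already destined for the listings, so no new data are needed. Reported worst grades may come out slightly less favourable, and they cannot come out more favourable.

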7.1.4 Analysis Software

All statistical analysis will be conduct by SAS 9.4 or later version.

7.1.5 Tables and listings

> Tables

In general, data will be summarized by group (i.e., low dose, high dose and placebo). The groups will be presented in columns.

> Listings

Unless otherwise specified, dose level and subject number will always be included in listings. The EDC original data will be displayed in priority. All listings will be sorted first by dose level, then by subject number and finally, if applicable, by visit number and/or a relevant date (e.g. date of onset of AE).

7.2 Subejct Dispositions

The number and percentage of subjects randomized and subjects in the FAS/PPS/SS will be presented by group.

The number and percentage of subjects discontinued from the study with a summary of the primary reason will be presented by group. The number and percentage of subjects in all of the analysis sets will be summarized by group.

The subjects, who fail screening, discontinue and excluded from analysis sets will be listed, respectively.

The compliance (including whether complete the whole course of immunization, whether complete the immunogenicity and CMI blood collection according to the protocol requirements, and whether complete follow-up as required by the protocol) will be summarized by group.

7.3 Demographics and baseline Characteristics

Descriptive statistics will be used to summarize demographics and baseline variables as follows:

- > Demographics: including age, gender, race, Chinese nationality, height and weight,
- Clinical characteristics: including travel history and contact history,
- Blood Virus Screening (HIV), nasopharyngeal swabs for SARS-CoV-2 testing, Blood for SARS-CoV-2 Testing,

- Baseline of physical examinations,
- Baseline of vital signs,
- ▶ Baseline of 12-lead ECG and chest CT scan,

Baseline is defined as the last available value prior to the prime immunization.

Prior and/or concomitant diseases and surgery history will be coded using Medical Dictionary for Regulatory Activities Version 23.0 (MedDRA 23.0), and they will be classified and summarized by System Organ Classification (SOC) and Preferred Term (PT). Prior medication, vaccination in the past 4 weeks and concomitant medication will be coded using World Health Organization Drug Dictionaries Version Q1 2020 (WHO-DD Q1 2020), and summarized and presented by ATC2 and drugname.

Listing of prior and/or concomitant diseases, surgery history, prior medication, vaccination and concomitant medication will be provided.

7.4 Immunogenicity Analyses

Descriptive statistics, including geometric mean and 95% confidence intervals (CIs), for GMT and GMFI of anti-S1 IgG antibody at all post-baseline time points will be presented by group.

The number and percentage of subjects with seroconversion of anti-S1 IgG antibody will be summarized by group for all post-baseline time points. The 95 % confidence interval of percentage will be calculated by Clopper-Pearson method.

The geometric mean of anti-S1 IgG antibody at each time points will be plotted in log-scale. The reverse cumulative distribution plot is to display S1 IgG antibody distribution at each time points by group.

The same statistical methods as anti-S1 IgG antibody and seroconversion rate will be conducted to analyze anti-RBD IgG antibody and SARS-CoV-2 neutralizing antibody (based on true virus' SARS-CoV-2 neutralizing test).

7.5 Exploratory analyses

7.6 Safety Analyses

7.6.1 Adverse Events

All AEs will be coded using the recent version of MedDRA Version 23.0, and be summarized by SOC and PT. Additionally, solicited AEs, including systematic AEs and local AEs predefined in the protocol, will be summarized. The severity of AEs will be analyzed under China NMPA Guidance (Refer to Appendix B in the protocol: *NMPA Guidance for Adverse Events Grading Scale for Preventive Vaccine Clinical Trials in China*), and that of adverse reactions will also be analyzed under US Food and Drug Administration (FDA) Guidance (Refer to Appedix C in the protocol: *FDA Toxicity Grading Scale in Preventive Vaccine Clinical Trials*) in addition to China NMPA guidance.

This study is mainly to analyze Treatment Emergent Adverse Events (TEAEs), which are defined as any AEs with an onset on or after the first immunization (if the AE was absent before the first immunization) or worsened after the first immunization (if the AE was present before the first immunization). The Non-TEAEs occur before the first immunization will not be included in the analysis, but will be listed. Unless particularly stated, AEs mentioned in below text are TEAEs.

All solicited AEs, including systematic and local AEs, will be graded based on the criteria given in "NMPA Guidance for Adverse Events Grading Scale for Preventive Vaccine Clinical Trials in China". And all related systematic and local reactions will be graded at the same time according to "US FDA Guidance for Industry. Toxicity Grading Scale for Healthy Adult and Adolescent Volunteers Enrolled in Preventive Vaccine Clinical Trials". The solicited systematic and local reactions will be analyzed based on both NMPA and US FDA guidance.

The episodes of AEs, number and percentages of subjects who experience at least one TEAE as follows will be presented by group:

- Overall Summary of Adverse Events
- > Any TEAEs by SOC and PT
- Related TEAEs by SOC and PT
- Unrelated TEAEs by SOC and PT
- > Any TEAEs by Solicited and Unsolicited AEs
- Related TEAEs by Solicited and Unsolicited AEs
- Unrelated TEAEs by Solicited and Unsolicited AEs
- ➢ Grade≥3 TEAEs by SOC and PT, according to China NMPA guidance

- ➢ Grade≥3 related TEAEs by SOC and PT, according to China NMPA guidance
- ➢ Grade≥3 Solicited Systematic and Local Reactions, according to China NMPA guidance
- ➢ Grade≥3 Solicited Systematic and Local Reactions, according to US FDA guidance
- > TEAEs leading to discontinuation by SOC and PT
- Related TEAEs leading to discontinuation by SOC and PT
- Unrelated TEAEs leading to discontinuation by SOC and PT
- ➢ AESIs by SOC and PT
- Related AESIs by SOC and PT
- Unrelated AESIs by SOC and PT
- ➢ TESAEs by SOC and PT
- Related TESAEs by SOC and PT
- > Unrelated TESAEs by SOC and PT

The DLT AE and related DLT AE will be summaried by group. The distribution of severity, injection stage, occurrence will be provided for TEAEs and related TEAEs. The episodes of AEs, number and percentage of subjects with TEAEs will be summarized by worst grade by PT nested within SOC.

For each solicited reaction (including fever), the number and percentage of subjects with TEAEs within 14 days after each immunization will be summarized by severity and overall.

TEAE after each immunization will be summarized based on Safety Set for prime and boost immunization, respectively.

The following TEAEs will be listed by subject: related TEAEs, unrelated TEAEs, TEAEs leading to discontinuation, AESIs and SAEs.

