#### 10.1.2 Solicited reactions

The occurrence of selected indicators of safety will be measured/collected for 14 days after each vaccination (including the days of vaccine vaccination), see details in following **Table** 5.

Table 4 Solicited local and systemic reactions

Local reactions (vaccination site):	Pain/tenderness
	Erythema/redness
	Induration/swelling
Systemic reactions:	Fever (a)
	Nausea
	Vomiting
	Diarrhea

Headache
Fatigue
Myalgia
Arthralgia
Chills
Loss of appetite
Malaise

(a) Based on recorded body temperature, fever is defined as axillary temperature ≥37.3°C.

The intensity of solicited safety parameters will be assessed respectively as described in grading scale of Appendix B and C.

Solicitation adverse reactions: there is at least a reasonable possibility of a causal relationship between vaccines and adverse events, that is, causality cannot be ruled out.

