# 10.3 Assessment of safety parameters

# 10.3.1 Assessment of intensity

Reaction signs and symptoms involved in the grading scale will be graded respectively by the investigator according to the Guidelines for Adverse Event Classification Standards for Clinical

Trials of Preventive Vaccines of NMPA (Appendix B) and FDA (Appendix C). AEs uninvolved in the grading scale will be graded clinically by the investigator according to following criteria. Grading and seriousness need to be assessed independently for each AE recorded on the CRF.

Mild	Grade 1	Lasting for a short time (<48h) or slight discomfort, which do not influence activity and no treatment is needed.
Moderate	Grade 2	Mild or moderate limitation of activity, which may require hospital visit, does not require or only requires mild treatment.
Severe	Grade 3	Obvious limitation of activity, which requires hospital visit and treatment, possibly requires hospitalization.
Critical	Grade 4	Possibly life-threatening; serious limitation of activity, which requires intensive care
Death	Grade 5	

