# 10.3.2 Relationship to investigational drug

Relatedness (causality) to vaccine will also be assessed by the investigator. The relationship between each AE, including solicited systemic AEs (solicited local AEs are considered as related) to trial vaccine(s) will be assessed using the following categories:

- Definitely related: There is reasonable time relationship between drug administration and the occurrence of adverse event; after drug withdrawal, the adverse reaction disappears or is rapidly relieved and improved (ie, dechallenge positive); when the drug is administrated again, the adverse event appears again (ie, rechallenge positive) and may get worse obviously; meanwhile, there is evidence from investigator brochure or literature data; besides, influence from original disease and other confounding factors are excluded.
- Probably related: There is no history of repeated drug administration. The rest are the same as those for "definitely related", or even if there is drug combination, the possibility of adverse reaction resulted from drug combination is generally excluded.
- Possibly related: There is close relationship between drug administration and adverse event, which can also be proved by literature data. However, there may be more than one drug which causes adverse event or the original disease progression cannot be excluded.
- Possibly unrelated: The relationship between adverse event and medication time is not close. The clinical manifestation is not consistent with the known adverse events of the drug. If the original disease develops, it may have the similar clinical manifestation.
- Unrelated: No drug is administrated, or there is no association between drug administration and the occurrence time of adverse event or there is other definite reason which results in adverse event.

Related, probably related and possibly related are listed as related to the investigational vaccine.

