2.3 Summary of Statistical Analysis Changes to the Protocol

The analyses described in this analysis plan are consistent with the analyses described in the study protocol.

3 Objectives

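### SAP 7.6.1 assigns FDA-scale grades to related reactions where the protocol grades all solicited reactions on both scales, so solicited systemic reactions judged unrelated could be missing from the FDA-scale severity tables

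*SAP*

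**What the plan says.** SAP 7.6.1 defines the two grading populations in consecutive sentences. For the NMPA scale: "All solicited AEs, including systematic and local AEs, will be graded based on the criteria given in" the Chinese guidance. For the FDA scale: "all related systematic and local reactions will be graded at the same time according to" the US guidance. The opening paragraph of 7.6.1 makes the same split, with adverse events under NMPA and adverse reactions also under FDA. SAP 7.1.2 writes its rule for events that reach grade 1 on one scale but not the other for related TEAEs only, and notes that a grade below 1 is stored as null.

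The same section then drops the condition. The following sentence reads "The solicited systematic and local reactions will be analyzed based on both NMPA and US FDA guidance", and the list of tables includes Grade 3 or higher "Solicited Systematic and Local Reactions, according to US FDA guidance", with a twin under NMPA.

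The protocol sets no causality condition. Section 10.1.2: "The intensity of solicited safety parameters will be assessed respectively as described in grading scale of Appendix B and C". Section 10.3.1: "Reaction signs and symptoms involved in the grading scale will be graded respectively by the investigator", on the NMPA and FDA scales. Section 13.1.4 lists any, related, Grade 3 or higher, and related Grade 3 or higher reactions as separate rows. Section 10.3.2 has the investigator assess causality for solicited systemic events, while "solicited local AEs are considered as related". SAP 2.3 states: "The analyses described in this analysis plan are consistent with the analyses described in the study protocol".

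**The concern.** The primary endpoints are the occurrence of solicited local and systemic reactions within 14 days of each dose, whatever the cause. A causality filter on one of the two severity scales is a departure from the protocol that the SAP does not declare.

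Two things are at stake. First, a reader who compares the NMPA and FDA Grade 3 or higher tables will take any gap as a difference between scales, when part of it may come from a difference in which events were graded. Second, the FDA-scale counts of systemic reactions would depend on the investigator's causality call. The investigator is blinded, but reactogenicity may hint at the arm: Protocol 4.2.4.1 reports that in the US study chills, muscle pain and joint pain occurred in vaccinees and not on placebo, and that 9 of 12 subjects on 30 µg had fever of at least 38.0 °C after the second dose.

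**Working it through.** **1. Where the condition appears**

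- SAP 7.6.1, opening paragraph: FDA scale for adverse reactions, as distinct from adverse events.
- SAP 7.6.1, grading sentences: NMPA for all solicited events, FDA for related reactions.
- SAP 7.1.2, scale-discrepancy rule: related TEAEs only.
- SAP 7.6.1, analysis sentence and FDA table title: no condition.
- Protocol 10.1.2 and 10.3.1: both scales, no condition.
- Protocol 13.1.4: related reactions are a row of their own, so the word reaction does not already imply relatedness there.

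Three places in the SAP carry the restriction and two omit it. The protocol's grading rules do not carry it.

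**2. Which reactions are exposed**

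The local items (pain/tenderness, erythema/redness, induration/swelling) are related by default and cannot be filtered out. The 11 systemic items are each subject to a causality call. Eight of them have their own row in Protocol Appendix C (seven in Table 2, fever in Table 3).

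**3. Effect on seeing a reaction at all**

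The plan's own figure (Protocol 13.3, SAP 4.3): the probability of at least one event in 24 subjects at rate p is 1 − (1 − p)^24. With p = 0.08, 1 − 0.92^24 = 0.8648, which agrees with the stated 86.5%.

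If only a share s of such reactions is called related, and each affected subject has one reaction, the rate that reaches the FDA table is 0.08 × s:

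- s = 0.75: 1 − 0.94^24 = 0.7735
- s = 0.50: 1 − 0.96^24 = 0.6246
- s = 0.25: 1 − 0.98^24 = 0.3842

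The shares are assumptions; the documents give none for solicited reactions.

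**4. Possible effect between arms**

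Apparent difference = (true vaccine rate × share called related on vaccine) − (true placebo rate × share called related on placebo). The documents give no placebo rate for systemic reactions, so the rates below are assumed. Take equal true rates, a share of 1 on vaccine, and a share of 0.75 or 0.50 on placebo:

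- 10% in both arms: 10 − 7.5 = 2.5 points, or 10 − 5 = 5 points
- 25% in both arms: 25 − 18.75 = 6.25 points, or 25 − 12.5 = 12.5 points (6 against 3 of 24)
- 40% in both arms: 40 − 30 = 10 points, or 40 − 20 = 20 points

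Swap the shares and every sign reverses. With all reactions graded, the shares drop out and each difference is 0. The sums apply to a row for one reaction. In a row for any systemic reaction, a subject with one related event stays in, so the effect would be smaller.

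**5. What the documents say on direction**

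Protocol 4.2.4.1 gives, for the US study, subjects with any AE (6/12, 6/12, 7/12, 1/9) and with a related AE (3/12, 6/12, 6/12, 1/9) at 10, 30 and 100 µg and on placebo. The related share of those with any AE is therefore 3/6, 6/6, 6/7 and 1/1. These counts are tiny and concern AEs in general. The share differs between groups, but the one placebo event was called related and the lowest share is in a vaccine arm.

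**The case against.** The SAP nowhere says that only related reactions receive an FDA grade. The analysis sentence and the FDA table title carry no condition, although other titles in the same list do use the word related. The summary of each solicited reaction by severity has no causality filter either. Protocol terminology is itself mixed: the end of 10.1.2 defines solicited adverse reactions by a reasonable possibility of causality. All of this stands, and it is why the conclusion is that such reactions could be missing, not that they will be. It does not remove the problem. The contrast between all and related in adjacent sentences is hard to read any other way, SAP 7.1.2 repeats it, and Protocol 13.1.4 separates related from all reactions.

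A reader might go further and infer that the filter removes events mainly from placebo and so inflates the vaccine-placebo contrast. The documents do not support that. Investigators are blinded, possibly related counts as related (Protocol 10.3.2), and Protocol 10.5 names fever, chills, headache and myalgia as expected after RNA vaccination, which gives reason to call them related in any arm. The US counts do not show placebo losing events.

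A reader might also infer that the primary safety result is compromised, or that the FDA scale is the one used abroad. Neither is established. Occurrence and NMPA severity are reported for all solicited events, and both related and unrelated TEAEs are tabulated and listed. Protocol 4.2.4.1 gives a 38.0 °C fever threshold, which matches Appendix C, but names no grading scale for the foreign study.

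**Conclusion.** The SAP is wrong as written on a narrow point and should be corrected. Its grading rule for the FDA scale departs from the protocol without being declared, and it conflicts with the SAP's own analysis sentence and table title. Followed literally, it makes the FDA-scale tables of solicited systemic reactions depend on a causality call, and gives the two Grade 3 or higher tables different event populations under the same title.

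The reach is limited to FDA-scale severity of solicited systemic reactions. Local reactions, NMPA-scale tables and overall occurrence are unaffected, and SAP 7.1 plans no formal testing. The size and direction of any between-arm distortion are unknown. The 2.5 to 20 points above illustrate what unequal attribution could do under assumed rates and shares, and are not an estimate for this trial.

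A related practical risk is that an unrelated reaction left without an FDA grade could look the same in EDC as one below FDA grade 1, since SAP 7.1.2 treats the latter as null.

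**What to change.** - **SAP 7.6.1:** delete the word related from the FDA grading sentence and, in the opening paragraph, replace adverse reactions with solicited reactions. State that all solicited local and systemic reactions within 14 days of each dose are graded and tabulated on both scales irrespective of causality, with related reactions as an additional row, as in Protocol 13.1.4.
- **SAP 7.1.2:** extend the scale-discrepancy rule to all solicited reactions.
- **EDC check:** confirm that FDA grades are recorded for reactions judged unrelated, so that a missing grade can be told apart from a grade below 1.
- If the restriction is intended, declare and justify it in SAP 2.3 and put related in the FDA table titles. This is the weaker option, because the tables would still depend on the causality call.

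The cost is SAP wording, table programming and one data check. Protocol 10.3.1 already has the investigator grade on both scales, so no new visits or assessments are needed. If the check finds ungraded reactions, the gaps should be filled from source records before unblinding.
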